3. To measure VE using other outcome measures such as against all episodes of *Pf malaria with symptoms* and *Pf malaria* rather than against the first episode, using proportional analysis, or using ITT or ATP populations, or severity of malaria infections or hemoglobin concentration.
4. To explore the relationship between detectable parasitemia prior to vaccination and VE.

Endpoints:

Primary Endpoints:

1. Proportion of vaccinees compared to controls experiencing related SAEs from V1 to 26 weeks after V3
2. VE computed as one minus the estimated hazard ratio (HR) (time-to-event analysis) for first episode of *Pf malaria with symptoms* from 2 weeks after V3 to 26 weeks after V3 in the modified ITT (mITT) population.

Secondary Endpoints:

1. Safety and tolerability in children
 - The differences in proportions of vaccinees compared to controls experiencing unsolicited AEs from the time of V1 to 14 days after V3 (or last immunization).

- The differences in proportions of vaccinees compared to controls experiencing laboratory abnormalities from time of V1 to 14 days after V3.
- The differences in proportions of vaccinees compared to controls experiencing solicited Aes during the 7 days following each immunization.
- 2. VE computed as one minus the estimated hazard ratio (HR) for first episode of *Pf malaria* detected by thick blood smear (TBS), from 2 weeks after V3 to 26 weeks after V3 in the mITT population.
- 3. Antibody levels to PfCSP by standardized ELISA comparing protected and unprotected vaccinees and controls.

Exploratory Endpoints:

- 1. Humoral and cellular immune responses to PfSPZ Vaccine
- 2. Genotyping of peripheral blood Pf parasites
- 3. Additional measures of VE
 - VE against all episodes (rather than first episode) of *Pf malaria with symptoms* and *Pf malaria* by Cox regression analysis
 - VE computed by proportional (binary) analysis (1 – risk ratio) for first episode of *Pf malaria* detected by TBS, from 2 weeks after V3 to 26 weeks after V3 in the intention-to-treat (ITT), mITT and according to protocol (ATP) populations (whole group and subgroups)
 - VE computed as one minus the estimated HR for first episode of *Pf malaria* detected by TBS, from 2 weeks after V3 to 26 weeks after V3 in the ITT and ATP populations (whole group and subgroups)
 - VE for *Pf malaria* measured by and nucleic acid detection in children from 2 weeks after V3 to 26 weeks after V3 using both (time to event, proportional/binary)

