These findings in pediatric studies are illustrative of the findings in all trials of PfSPZ Vaccine, including all nine randomized, double-blind, normal saline placebo-controlled trials that have been completed and unblinded. None of these trials has shown any differences in the rates of any AEs between vaccine recipients and controls after unblinding (#5, 7, 8, 9, 10, 12, 14, 15 in **Table 3**) (Jongo S, unpublished; Sissoko M and Healy S, unpublished; Oneko M and Steinhardt L, unpublished)([3-10](#)) except for one study where there was an excess of myalgia in the vaccine group (#10 in **Table 3**). Most importantly, there were no age or dose effects on the rates of AEs with doses as high as 1.8×10^6 PfSPZ in infants and young children ([3](#), [10](#)). There also has not been an increase in AEs with repeated dosing (i.e., the rates of AEs after second or third doses have been similar to the rates after first dose). It is thus not clear that PfSPZ Vaccine has consistently caused *any* adverse reactions at the doses tested to date. In addition, there have been no allergic reactions linked to the vaccine. A few volunteers have developed urticarial rashes in the days following immunization, but in no cases have these rashes been clearly linked to the vaccine.

A meta-analysis of AE data is shown for children using forest plots of total solicited AEs in vaccinees and placebos in the randomized, double-blind, placebo-controlled trials analyzed to date (**Figure 8**). In all cases, 95% confidence intervals cross a ratio of 1, indicating no differences between vaccinees and controls.

Figure 8. Effect of vaccine on incidence of any solicited systemic adverse events per study subject in randomized, double-blind, placebo-controlled trials of PfSPZ Vaccine in infants and children aged 5 months to <18 years in sub-Saharan Africa.

Trial sites included: Bagamoyo, Tanzania (BSPZV2); Siaya, Kenya (KSPZV1b); and Bioko Island, Equatorial Guinea (EGSPZV2). #Vac. is the number of subjects enrolled in the vaccine arm in each study; # Plac. is the number of subjects enrolled in the NS control arm of each study. Numbers in parentheses are the number of subjects experiencing the AE after any of the injections administered. V = vaccine recipients, NS = normal saline recipients, OR = odds ratio, LCL = lower confidence limit, UCL = upper confidence limit. Weight is based on sample size and is represented by the width of the blue bar.

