4. OBJECTIVES AND ENDPOINTS

OBJECTIVES	ENDPOINTS	JUSTIFICATION FOR ENDPOINTS
Primary		
To describe the safety of PfSPZ Vaccine in children with respect to the occurrence of possibly, probably, or definitely related serious adverse events (SAEs).	Proportion of vaccinees compared to controls experiencing related SAEs from V1 to 26 weeks after V3	SAEs potentially represent the most important adverse vaccine reactions.
To measure VE against first episode of Pf malaria with symptoms by time-to-event analysis.	VE computed as one minus the estimated hazard ratio (HR) for first episode of Pf malaria with symptoms from 2 weeks after V3 to 26 weeks after V3 in the modified ITT (mITT) population.	Time-to-event analysis is standard in the malaria vaccine field and takes into account how many subjects develop first Pf malaria with symptoms and time for this to happen.
Secondary		
To assess the safety of PfSPZ Vaccine with respect to the occurrence of unsolicited AEs, laboratory abnormalities, solicited AEs.	
Safety and tolerability in children:
 
 - The differences in proportions of vaccinees compared to controls experiencing unsolicited AEs from the time of V1 to 14 days after V3 (or last immunization). - The differences in proportions of vaccinees compared to controls experiencing laboratory 	These endpoints could potentially reveal the occurrence of adverse vaccine reactions.

OBJECTIVES	ENDPOINTS	JUSTIFICATION FOR ENDPOINTS
	abnormalities from time of V1 to 14 days after V3. - The differences in proportions of vaccinees compared to controls experiencing solicited AEs during the 7 days following each immunization.	
To measure VE against first episode of Pf malaria (parasitemia) with or without associated symptoms by time-to-event analysis.	VE computed as one minus the estimated hazard ratio (HR) for first Pf malaria (parasitemia) detected by TBS, from 2 weeks after V3 to 26 weeks after V3 in the mITT population.	TBS is the standard diagnostic method for detecting parasitemia. Time-to-event analysis is standard in the malaria vaccine field for measuring VE taking into account how many subjects develop first Pf malaria and time for this to happen.

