10.1 STATISTICAL HYPOTHESIS

Primary Endpoints

Safety: The primary safety endpoint is the proportion of vaccinees experiencing related SAEs from V1 to 26 weeks after V3. There is no formal hypothesis test associated with this primary safety endpoint. Rather, the proportion of subjects experiencing related SAEs will be presented for each arm separately using frequencies, percentages, and descriptive 95% confidence intervals (CIs).

Efficacy: the primary efficacy endpoint is the vaccine efficacy against *malaria with symptoms*. For this protocol, there is a primary and a secondary case definition of *Pf malaria with symptoms*.

The primary case definition is as follows:

Pf malaria with symptoms is defined as a positive thick blood smear at a density of >1000 P/uL plus:

- Measured axillary temperature ≥ 37.5 degrees Celsius or history of fever (subjective or objective) in the last 24 hours, or,
- Symptoms of malaria –
 - Verbal individual (individual able and willing to answer questions): A verbal individual is considered symptomatic if reporting at the time of evaluation at least two of the following symptoms/symptom groups: headache, chills and/or rigors, malaise and/or fatigue, dizziness and/or light-headedness, myalgias and/or arthralgias; or
 - Non-verbal individual (small child or any individual unable or unwilling to answer questions): A non-verbal individual is considered symptomatic if manifesting at the time of evaluation at least two of the following signs/sign groups: drowsiness, irritability and/or fussiness, inability and/or refusal to eat or drink, prostration; or
- Any individual: Signs of severe malaria (e.g. impairment of consciousness, severe anemia, hemoglobinuria, acute kidney injury, etc.).

The secondary case definition is as follows:

Pf malaria with symptoms is defined as a positive thick blood smear at a density of > 0 P/uL plus:

- Measured axillary temperature ≥ 37.5 degrees Celsius or history of fever (subjective or objective) in the last 24 hours, or,
- Symptoms of malaria as defined in the primary case definition; or
- Meeting criteria for severe malaria

The formal hypothesis associated with the primary efficacy endpoint is a superiority test of

$$H_0: VE = 0 \text{ versus } H_A: VE < > 0$$

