3.1 Safety Analyses

The primary safety endpoint is the occurrence of an SAE between V1 and 26 weeks after V3 which is at least possibly related to treatment. Serious AEs which meet this definition will be summarized in frequency tables and listings according to system organ class, preferred term, relatedness, and severity. The primary safety analysis will be performed using the ITT population and according to treatment received at V1, regardless of any randomization or allocation errors. All SAEs will be coded using the Medical Dictionary for Regulatory Activities (MedDRA) and summarized using frequencies, proportions, and exact 95% CIs for proportions. Rates of SAEs (overall and for any system organ class or preferred term with at least 5 events in either group) will be compared using two-sided 0.05 level Fisher's Exact Tests.

Secondary safety endpoints include the occurrence of unsolicited AEs, laboratory abnormalities, and solicited AEs in the ITT population. Unsolicited AEs documented from V1 to 14 days following V3 will be coded using MedDRA and summarized in frequency tables according to system organ class, preferred term, relatedness, and severity. Summaries will be provided overall and according to the vaccination number immediately prior to AE onset. Rates of unsolicited AEs (overall and for any system organ class or preferred term with at least 5 events in either group) will be compared using two-sided 0.05 level Fisher's Exact Tests. Adverse events leading to premature discontinuation from the study will be listed separately. Clinically relevant laboratory abnormalities recorded in the 14 days after V3 will be summarized in frequency tables by type, grade, and clinical relevance.

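### The secondary safety endpoints are defined as differences in proportions, but the plan never estimates a between-arm difference, so nothing bounds the excess of adverse events over control

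*SAP*

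**What the plan says.** **Endpoints.** Protocol section 2.1 lists as a secondary safety endpoint "The differences in proportions of vaccinees compared to controls experiencing unsolicited AEs from the time of V1 to 14 days after V3". It uses the same form for laboratory abnormalities, and section 4 repeats it, including for vaccinees compared with controls "experiencing solicited AEs during the 7 days following each immunization". The primary safety endpoint, related SAEs, is also worded there as vaccinees compared with controls.

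**Analyses.** Protocol 10.4.2 and SAP 3.1 are nearly identical:

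- SAEs are "summarized using frequencies, proportions, and exact 95% CIs for proportions". The plan then adds a between-arm test, in which the two arms' rates "will be compared using two-sided 0.05 level Fisher's Exact Tests". This is done for the overall rate and, separately, "for any system organ class or preferred term with at least 5 events in either group".
- Unsolicited AEs get frequency tables and the same Fisher comparison.
- For laboratory abnormalities: "Clinically relevant laboratory abnormalities recorded in the 14 days after V3 will be summarized in frequency tables by type, grade, and clinical relevance".
- Solicited AEs are named as a secondary endpoint, but no analysis is given.

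Neither document plans a risk difference, a risk ratio, a between-arm interval, a margin or a between-arm safety power.

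**Status of the SAE comparison.** Protocol 10.1 says of related SAEs: "There is no formal hypothesis test associated with this primary safety endpoint".

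**The concern.** An endpoint stated as a difference calls for an estimate of that difference and its uncertainty. For two kinds of event the plan supplies a p-value instead, and for the other two it supplies no comparison. A p-value above 0.05 does not tell the reader how large an excess is still compatible with the data. That is what matters in a trial meant to support Phase 3 testing in children, using a two-dose priming schedule that only one earlier paediatric study has used (Protocol section 8.1, pausing criteria). The background shows how such results can be read. Of the earlier paediatric trials, Protocol 3.3.1 says: "In all cases, 95% confidence intervals cross a ratio of 1, indicating no differences between vaccinees and controls".

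The SAE wording is a smaller, separate problem. One section says that there is no formal test, and two others apply one at a stated level.

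**Working it through.** **1. Endpoint against analysis**

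| Endpoint | Between-arm analysis planned | Interval planned |
|---|---|---|
| SAEs | Fisher p-value | Exact, per arm |
| Unsolicited AEs | Fisher p-value | None stated |
| Laboratory abnormalities | None | None stated |
| Solicited AEs | None stated | None stated |

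No row contains an estimate of the difference. This part needs no assumption about event rates.

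**2. The plan's own safety figures.** Protocol 10.2 gives operating characteristics for a single arm of 120, and those checked reproduce:

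- Chance of no event at a true rate of 1%: 0.99^120 = 0.299 (Table 13: 0.299).
- Exact upper limit for 0/120: 1 - 0.025^(1/120) = 0.0303 (Table 14: 0.030).

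These describe the absolute rate in one arm. They say nothing about vaccine minus control.

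**3. What the Fisher test can detect.** Inputs from the documents are 1:1 allocation (7.3.1), 120 per arm (10.2, safety calculations), about 134 per arm (10.2, planned enrolment) and a two-sided 0.05 level (10.4.2, SAP 3.1). Two inputs are assumptions: the control rate, varied below, and a doubling as the effect of interest.

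Power = sum over all x, y of Bin(x; n, 2p) × Bin(y; n, p) × 1[Fisher p ≤ 0.05], where p is the control rate. Miss rate = 1 - power.

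| Control → vaccine | Missed, n = 120 | Missed, n = 134 |
|---|---|---|
| 5% → 10% | 78% | 74% |
| 10% → 20% | 48% | 42% |
| 15% → 30% | 24% | 19% |
| 20% → 40% | 9% | 6% |

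Power reaches 50% at a control rate of 9.7% (n = 120) or 8.7% (n = 134), and 80% at 16.1% or 14.8%.

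A rough guide to plausible rates is Table 8 of the Protocol, pooled and still blinded, for 63 children aged 7–12. If each child is counted at one grade only, it gives chills 1 (1.6%), objective fever 4 (6.3%), fatigue 6 (9.5%) and headache 10 (15.9%). These are solicited events from another trial with both arms combined, so they only suggest that many single terms lie in the low-power range.

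**4. What an interval would add.** Take 12/120 against 6/120, a difference of 5.0 points.

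- Fisher p = 0.22.
- Wilson limits are 0.0581 to 0.1667 for 12/120 and 0.0231 to 0.1048 for 6/120.
- Newcombe lower limit: 0.05 - √[(0.10 - 0.0581)² + (0.1048 - 0.05)²] = -0.019.
- Newcombe upper limit: 0.05 + √[(0.1667 - 0.10)² + (0.05 - 0.0231)²] = +0.122.
- The Miettinen-Nurminen interval is -1.8 to +12.2 points.

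Under the plan the reader sees p = 0.22. With the interval, the reader also sees that an excess of 12 points is not excluded.

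Even with equal observed rates the limits are wide. At 120 per arm the Newcombe upper limits are +3.1 points at 0/120 in each arm, +6.1 at 6/120, +7.9 at 12/120 and +10.1 at 24/120.

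**The case against.** Several stronger readings are tempting, and the documents do not support them.

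- **That the Fisher test generally misses a doubling half the time or more.** This depends on a control rate that the documents do not give. It holds up to about 9–10% and fails above that. It may fit single terms, but not an overall AE rate that is common.
- **That harm is left unbounded.** SAEs have exact per-arm intervals, which bound the absolute rate in vaccinees. Only the excess over control is unbounded.
- **That a related-SAE signal would be lost.** The pausing criteria in Protocol section 8.1 are triggered by one related SAE in a vaccinee, apart from expected events due to malaria or its treatment, and lead to DSMB review. At a true rate of 3% the chance of at least one event among 120 is 1 - 0.97^120 = 97%. Detecting such a signal does not rest on Fisher's test.
- **That non-significance will be reported as no difference.** No such rule appears in SAP 3.1 or Protocol 10.4.2. The sentence in Protocol 3.3.1 concerns earlier trials and reads odds ratios with confidence limits. The summary in the same section is more cautious: it says that the side-effect profile could change as better-powered trials report.
- **That the five-event filter is itself a defect.** A 5 versus 0 split at 120 per arm passes the filter with p = 0.060, but the filter does not change the power figures above.

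The conflict with 10.1 can also be argued away in part, because 10.1 concerns related SAEs and the Fisher comparison may be meant for all SAEs. Finally, per-arm counts will be tabulated, so a reader could derive the differences.

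These points narrow the concern. None of them supplies the missing estimate, gives solicited AEs an analysis, or tells the reader whether the SAE test is formal.

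**Conclusion.** The concern holds in this form. The secondary safety endpoints are differences in proportions, the plan estimates none of them, and the excess over control is not bounded for any safety endpoint. This follows from the text alone.

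The size of the loss where Fisher tests are used is conditional. On assumed control rates, with 134 and 120 per arm, a doubling is missed 74–78% of the time at 5%, 42–48% at 10%, 19–24% at 15% and 6–9% at 20%. For laboratory abnormalities and solicited AEs the gap is wider, because no between-arm comparison is planned at all.

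The statements in 10.1 and in 10.4.2 with SAP 3.1 about testing SAEs need to be reconciled. This is a reporting and analysis weakness that should be corrected before unblinding. It does not show that the vaccine's safety would be misreported.

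**What to change.** In SAP 3.1 and Protocol 10.4.2:

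1. For related SAEs, unsolicited AEs, solicited AEs and laboratory abnormalities, over the windows in the endpoint definitions, report the vaccine-minus-control risk difference with a two-sided 95% Miettinen-Nurminen (or Newcombe) interval. Name one method in advance.
2. Keep any Fisher p-values as descriptive flags.
3. State that a non-significant test is not evidence of no difference.
4. Label the SAE comparison as descriptive, so that 10.4.2 and SAP 3.1 agree with 10.1.

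The cost is wording in two documents and one more table column, with no change to data collection. The downside is that the report must show wide upper limits, for example about 6 points when 6/120 have the event in each arm.

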Table 9. Laboratory abnormalities Grade 2 or higher by age group, days 1 to 28 post-immunization.

Tests were scheduled 1 and 7 days after each vaccine dose and prior to V3. The table also includes any unscheduled lab tests. Data from vaccine and normal saline placebo groups combined (trial remains blinded). Data are the number of participants experiencing the abnormalities and also the number of abnormalities experienced (no child had more than one lab abnormality of a given type).

Laboratory abnormality	Severity Grade	1-2 years (n=36)	3-6 years (n=101)	7-12 years (n=63)
ALT elevation	Grade 2 or higher	0	0	0
Creatinine elevation	Grade 2	0	0	1
	Grade 3 or higher	0	0	0
Hemoglobin decrease	Grade 2 or higher	0	0	0
WBC decrease	Grade 2 or higher	0	0	0
Platelet count decrease*	Grade 2	0	0	1
	Grade 3	1	2	0
	Grade 4	0	0	1

[figure not shown]
*All Grade 3 and 4 platelet count abnormalities occurred 1 day after immunization (two episodes with dose 1, 1 with dose 2, 1 with dose 3). Preceding values normal in all cases. Follow-up tests also normal in all cases, performed after 4 days (Grade 3), 5 days (Grade 3 and Grade 4), 6 days (Grade 3) and 21 days (Grade 2). There were no repeat episodes of decreased platelet counts with subsequent dosing. Toxicity scale criteria: Grade 2 creatinine elevation: > 88-141 µmol/L; Grade 2 platelet count: 51-75,000/µL Grade 3 platelet count: 25-50,000/µL; Grade 4 platelet count: < 25,000/µL

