Local reactogenicity (secondary to PfSPZ Vaccine/normal saline) – through Day 7 post injection	
Injection site pain/tenderness	Injection site induration
Injection site erythema/redness	Injection site swelling/edema
Injection site pruritus	Injection site bruising
Limitation of arm movement	
Systemic reactogenicity (secondary to PfSPZ Vaccine/normal saline) – through Day 7 post injection – for children able to express themselves verbally	
Rash	Urticaria
Generalized pruritus	Generalized Edema
Headache	Fever or feverish
Chills	Malaise/Fatigue
Myalgia	Arthralgia
Sweats	Diarrhea
Back Pain	Chest Pain (non-musculoskeletal)
Nausea/Vomiting	Abdominal Pain
Systemic reactogenicity (secondary to PfSPZ Vaccine/normal saline) – through Day 7 post injection – for averbal children	
Rash	Urticaria

Generalized pruritus	Generalized Edema
Drowsiness	Fever or feverish
Inability/refusal to eat or drink	Irritability/fussiness
Nausea/Vomiting	Diarrhea
Symptoms to be solicited during malaria monitoring phase – study days 43 through 211	
Headache	Chills/rigors
Malaise/fatigue	Dizziness/lightheadedness
Myalgias/arthalgias	Fever or feverish

¹ Note absolute lymphocyte counts and absolute eosinophil counts will be captured on CRFs for use for research assessments. If clinically significant changes as determined by PI, these may also be reported as AEs.

Any laboratory abnormalities (other than those specified as safety labs in the protocol as defined by the values in the toxicity table) should be reported as AEs if they require intervention. Interventions include, but are not limited to, discontinuation of treatment, dose reduction/delay, additional assessments, or concomitant treatment. In addition, any medically important laboratory abnormality may be reported as an adverse event at the discretion of the investigator. This could include a laboratory result for which there is no intervention, but the abnormal value suggests a disease or organ toxicity. In addition, similar to solicited AEs, all laboratory AEs will be collected and graded for severity through 7 days after each vaccination until resolved.

The Investigator will assess all AEs with respect to **Seriousness** (criteria listed above), **Severity** (intensity or grade), and **Causality** (relationship to study agent and relationship to research) according to the following sections in the protocol.

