Arthralgia	No interference with activity	Some interference with activity	Significant; prevents daily activity	ER visit or hospitalization
Nausea/ Vomiting	No interference with activity or 1 – 2 episodes/24 hours	Some interference with activity or > 2 episodes/24 hours	Prevents daily activity, requires outpatient IV hydration	ER visit or hospitalization for hypotensive shock
Seizures- includes new or pre-existing febrile seizures	NA	NA	Seizure(s) that are not prolonged or repetitive	Prolonged and repetitive seizures (e.g., status epilepticus) OR Difficult to control (e.g., refractory epilepsy)

Abbreviations: ER, emergency room; IV, intravenous; PO, “per os” or oral administration.

¹ The definitions provided in the table are modified versions taken from the FDA Guidance for Industry “Toxicity Grading Scale for Healthy Adults and Adolescent Volunteers Enrolled in Preventive Vaccine Clinical Trials” dated September 2007 and DAIDS Table for Grading the Severity of Adult and Pediatric Adverse Events version 2.1 July 2017.

Mali Laboratory AE Grading for Pediatric Population

Hematology and Biochemistry Values ^{1, 2}	Mild (Grade 1)	Moderate (Grade 2)	Severe (Grade 3)	Potentially Life Threatening (Grade 4)
Hemoglobin (Male/Female) - gm/dL	7.5 – 8.4	6.1 – 7.4	5.0 – 6.0	< 5.0 g/dL
WBC Increase - 10³/µL	14.5 – 16.0	16.1 – 20.0	20.1 – 30.0	>30.0
WBC Decrease - 10³/µL	2.5 – 3.3	1.5 – 2.4	1.0 – 1.4	< 1.0 with or without fever
Neutrophil/Granulocyte Decrease³ - 10³/µL	0.75 – 0.99	0.50 – 0.74	< 0.50	< 0.50 with fever
Platelets Decreased - 10³/µL	100 – 120	70 – 99	25 – 69	< 25
Creatinine (Male/Female) - µmol/L	95.00 – 119.99	120.00 – 149.99	150.00 – 200.00	> 200.00 and requires dialysis
Liver Function Tests/ALT - U/L	75.0 – 150.9	151.0 – 300.9	301.0 – 600.0	> 600.0

Abbreviations: ALT, alanine transaminase; WBC, white blood cell.

¹ The laboratory values provided in the tables serve as guidelines and are dependent upon institutional normal parameters. Institutional normal reference ranges should be provided to demonstrate that they are appropriate.

² The clinical signs or symptoms associated with laboratory abnormalities might result in characterization of the laboratory abnormalities as Potentially Life Threatening (Grade 4). For example, a low sodium value that falls within a grade 3 parameter should be recorded as a grade 4 hyponatremia event if the subject had a new seizure associated with the low sodium value.

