Appendix B: Institutional Normal Laboratory Values for Children

Hematology Reference Intervals*

	Reference Interval	Units
WBC- Leukocytes	4.8 – 11.2	$10^3/\mu\text{L}$
Hemoglobin	9.1 – 13.3	g/dL
Platelet Count	188 – 551	$10^3/\mu\text{L}$
Absolute Granulocyte Count	1.4 – 5.9	$10^3/\mu\text{L}$

*Based on children ranging in age from 5 to 9 years old (based on sampling done at Bancoumana and Doneguebougou research sites, Mali)

Biochemistry Reference Intervals*

	Reference Interval	Units
ALT	11.5 – 53.0	U/L
Creatinine	< 80.6	$\mu\text{M/L}$

*Based on children ranging in age from 5 to 9 years old (based on sampling done at Bancoumana and Doneguebougou research sites, Mali)

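### The only planned laboratory safety analysis is a table of toxicity grades, and for platelets, white cells and ALT those grades start well outside the local normal limits, so a general shift in vaccinees could go largely unseen; a baseline-adjusted comparison of measured values would be a cheap addition.

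*SAP*

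**What the plan says.** The protocol synopsis and Section 4 make laboratory safety a secondary endpoint: "The differences in proportions of vaccinees compared to controls experiencing laboratory abnormalities from time of V1 to 14 days after V3". The analysis is given in one sentence, with the same wording in protocol 10.4.2 and SAP 3.1. It covers "Clinically relevant laboratory abnormalities recorded in the 14 days after V3", which "will be summarized in frequency tables by type, grade, and clinical relevance". Fisher's exact test is specified for SAEs and unsolicited AEs, but no test is named for laboratory abnormalities. Neither document plans a mean, a change from baseline, a shift table or a count outside reference limits for platelets, white cells, ALT or creatinine.

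Grades come from the Appendix A table "Mali Laboratory AE Grading for Pediatric Population". Protocol 9.11.4 tells investigators how to report laboratory abnormalities "other than those specified as safety labs in the protocol as defined by the values in the toxicity table". That is an exception clause rather than a definition, but it shows that the protocol's own safety tests are judged against the toxicity table. Appendix B, "Institutional Normal Laboratory Values for Children", gives reference intervals from local children aged 5 to 9, sampled partly at the trial site. A footnote in Appendix A calls the grade limits guidelines that depend on institutional normal values.

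**The concern.** Several bands of values are outside the local normal range yet carry no grade: platelets 121-187, WBC 3.4-4.7 and granulocytes 1.0-1.3 (all x10³/µL), and ALT from just above 53 to 74.9 U/L. A grade table counts only the children who cross the whole band. A moderate fall shared by all vaccinees would leave most of them ungraded in both arms, and the report could then say that laboratory abnormalities did not differ.

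Section 4 justifies this endpoint as a way to reveal adverse vaccine reactions. The pausing-criteria section notes that this is only the second study to give children two priming doses a week apart, and draws from this the need to check safety laboratory tests. The measured values and a pre-V1 value are collected for every child, but the planned analysis uses neither.

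**Working it through.** **The plan's own safety figures.** For an arm of 120 and a true rate of 1%, Pr(0) = 0.99^120 = 0.299, Pr(1) = 120 × 0.01 × 0.99^119 = 0.363, and Pr(2+) = 0.338. These match Table 13. No power figure is given for the laboratory endpoint.

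**Step 1: the gap, from the two appendices alone.**

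| Test | Appendix B limit | Grade 1 starts at | Gap | Limit after a 25% fall |
|---|---|---|---|---|
| Platelets | 188 | 120 | 36% below | 141, ungraded |
| WBC | 4.8 | 3.3 | 31% below | 3.6, ungraded |
| Granulocytes | 1.4 | 0.99 | 29% below | 1.05, ungraded |
| Haemoglobin | 9.1 | 8.4 | 8% below | 6.8, Grade 2 |
| ALT (upper) | 53.0 | 75.0 | 42% above | not applicable |
| Creatinine (upper) | 80.6 | 95.0 | 18% above | not applicable |

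A child at the ALT upper limit whose value rises by a third reaches 53 × 4/3 = 70.7, also ungraded. This step needs no distributional assumption.

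**Step 2: how many children would be graded.** Assumption: each Appendix B interval is the central 95% of a log-normal distribution, and every vaccinee's value is multiplied by 0.75. Log SD = ln(upper/lower)/3.92, which gives platelets 0.274, WBC 0.216 and granulocytes 0.367. For platelets the geometric mean is √(188 × 551) = 322. The control z at 120 is ln(120/322)/0.274 = -3.60, or 0.016%. After the fall, z = -3.60 + 0.288/0.274 = -2.55, or 0.54%. The same method gives WBC 0.011% and 0.91%, and granulocytes 0.18% and 1.7%. In an arm of 120 that is about 0.7, 1.1 and 2.0 graded vaccinees.

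**Step 3: power of the grade table.** With 120 per arm, Fisher's test gives p = 0.060 for 5 v 0 and p = 0.029 for 6 v 0, so at least 6 v 0 is needed. By enumeration at 120 per arm:

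| | Platelets | WBC | Granulocytes |
|---|---|---|---|
| One panel | 0.01% | 0.1-0.2% | 1.4-1.6% |
| Three independent panels | 1.3-1.6% | 10-19% | 39-41% |

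Each range compares a cut at the printed Grade 1 limit with one half a reporting step above it (for example WBC 3.3 or 3.35). Three independent panels is the optimistic extreme, because a child's values are correlated over time. The daily blood volumes in the Schedule of Activities fit three post-dose panels, on Days 8, 22 and 43. Only Day 43 is scheduled in the SAP's window.

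**Step 4: sensitivity to the assumptions (one panel, 120 per arm).**
- *Normal instead of log-normal, 25% fall in each child:* power is 0.2%, 0.5% and 1.4%.
- *A fixed fall of 25% of the mean:* for platelets the mean is 369.5, the SD is (551 - 188)/3.92 = 92.6 and the fall is 92.4. Graded: 4.5% v 0.35%. Power is 35%, and 47% for both WBC and granulocytes. A child at 188 would then lose 49%, so this is not a 25% fall in every child.
- *Higher background:* Table 7 (Kenya, Day 8, any grade, grading scale not given) shows platelets 1.8-3.8%, WBC 2.7-5.7% and neutrophils 7.2-7.5%. If 1.8% of controls were below 120 because the whole platelet distribution sat lower, z = -2.10 + 1.05 = -1.05, so 14.7% of vaccinees would be graded and power would be 96%. But the median would then be 120 × exp(2.10 × 0.274) = 213, and about 32% of controls would be below 188, which contradicts Appendix B. If instead a separate 1.8% of unwell children supply the background, the comparison is 2.3% v 1.8% and power is about 1%.

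**Step 5: the measured values.** Power = Φ(|ln ratio|/SD × √60 - 1.96). For a 10% fall in platelets this is Φ(0.105/0.274 × 7.75 - 1.96) = 84%. WBC gives 97% and granulocytes 60%, before any gain from baseline adjustment. For a 25% fall all three exceed 99.9%. A count below the Appendix B lower limit after a 25% fall would be 18% (platelets), 26% (WBC) and 12% (granulocytes) against 2.5%, with Fisher power of 98%, over 99% and 77%.

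**The case against.** The strongest reply is that the stated endpoint is a proportion with abnormalities, the analysis is descriptive, and many values after a 25% fall are still normal (platelets of 300 would become 225). On that view a comparison of means is an enhancement rather than a correction. This stands, and it is why the point is put as a cheap improvement.

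The power figures also rest on a borrowed test, on a reading of Appendix B that the documents do not state, and on a background rate that the protocol itself suggests may be higher: the pausing-criteria section calls Grade 2 falls in blood counts common in African children. These objections stand as limits on the percentages. They do not touch Step 1.

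A third reply is that abnormalities can be reported outside the grade table. Protocol 9.11.4 allows any medically important value to be reported as an AE, and 8.2 mentions changes from baseline. Both act child by child at the investigator's discretion, so neither can show a moderate shift across an arm.

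A reader might infer that the trial's laboratory safety analysis as a whole is blind. The documents do not support that: a 25% fall in haemoglobin would grade 50-57% of vaccinees and would be seen almost with certainty.

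A reader might also infer from the Table 9 footnote that this scale is generally laxer than the one used in Gabon. It is not: for platelets, Grade 2 is 70-99 here and 51-75 there.

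Nor would the addition necessarily catch the Gabon platelet falls. The Grade 3-4 values were seen one day after dosing and were normal on retest 4 to 6 days later. This trial's panels fall 7 or 14 days after a dose, and a mean dilutes isolated deep falls, which a grade table counts.

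**Conclusion.** The point holds for platelets, WBC, granulocytes and ALT, less strongly for creatinine, and not for haemoglobin. From the appendices alone, any child who starts inside the reference interval can lose 25% of platelets or white cells without receiving a grade.

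Under the central-95%, log-normal reading with Fisher's test, power for a 25% fall in every vaccinee is below about 2% at one panel. With three independent panels it is about 2% (platelets), 10-19% (WBC) and 40% (granulocytes). A fixed-amount fall or a higher background could change these figures considerably. The supportable conclusion is low, assumption-dependent sensitivity to a general shift. A reader might go further and say that the table cannot detect such a shift at all. That is too strong, because exclusion criterion 3 admits some children below the local limits, and they could cross into Grade 1.

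**What to change.** Leave the grading scale, the grade tables and the pausing criteria as they are. Add to SAP 3.1:

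- For platelets, WBC, granulocytes, ALT and creatinine, a descriptive between-arm comparison of log values at each scheduled post-dose panel, adjusted for the pre-V1 value. Report it as a ratio of geometric means with a 95% CI, labelled as unadjusted for multiplicity.
- Counts by arm, at each panel, of values outside the Appendix B limits, so that out-of-range but ungraded results are visible.

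The cost is a paragraph of SAP text and a few tables on data already collected. The drawback is about 15 further descriptive comparisons (5 tests × 3 panels), some of which may look notable by chance.
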